13.3.2. Subject Disposition

An accounting of all consenting subjects will be provided at the end of the study. This will include a breakdown of subjects who consented, were treated, discontinued treatment, died, and were lost to follow-up or withdrew consent.

13.3.3. Baseline Subject and Disease Characteristics

A summary of subject demographics and disease-related characteristics will be completed and assessed.

13.3.4. Efficacy Analyses

13.3.4.1. Primary Analysis

Disease control rate will be estimated with the corresponding 95% Clopper-Pearson confidence interval. Evaluation of the primary objective will be made based on the rejection regions described in Section 13.1.

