5.2. Overall Study Design

This is a single arm, two-stage phase II study designed to evaluate disease control rate in subjects with metastatic appendiceal carcinomas who have had failure of initial fluoropyrimidine-based chemotherapy.

In the first stage, a total of 28 subjects in the evaluable population will be enrolled. Of these, if at least 8 should achieve disease control (Section 13.1.1) the study will continue on to the second stage. In the second stage, 11 participants in the evaluable population (total of 39) will be enrolled. If at least 16 of the 39 total subjects enrolled achieve disease control, then we will be able to reject the null hypothesis. The sample size of evaluable population for both Stage 1 and Stage 2 include participants who begin nintedanib therapy.

Following informed consent and eligibility check, subjects will be enrolled and treated with 200mg of oral nintedanib two times per day and undergo disease evaluation after two months. Subjects who progress will be discontinued from study treatment and those who do not progress will continue twice daily treatment with nintedanib and will continue to undergo disease evaluation every two cycles.

Data from this study will be collected on electronic case report forms (eCRFs) and stored in the clinical trials management system (CTMS).

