13. STATISTICAL CONSIDERATION

13.1 Sample Size

This study is a Simon (minimax) two-stage design that will enroll up to a total of 39 subjects. The primary endpoint is overall disease control. In the first stage, a total of 28 subjects in the evaluable population will be enrolled. Of these, if at least 8 should

achieve disease control (Section 13.1.1) the study will continue on to the second stage. In the second stage, 11 participants in the evaluable population (total of 39) will be enrolled. If at least 16 of the 39 total subjects enrolled achieve disease control then we will be able to reject the null hypothesis. The sample size of evaluable population for both Stage 1 and Stage 2 include participants who begin nintedanib therapy.

Given the lack of information of clear benefit of any therapy in the second line setting of subjects with appendiceal carcinoma, a disease control rate of 30% would be considered an inferred clinical historical rate. Alternatively, a 50% disease control rate which, if achieved, would be worthy of further investigation. Assuming a one-sided $\alpha = 0.10$ significance level, this design will provide at least 90% power to reject the null hypothesis, assuming the true disease control rate is 50%.

Endpoint Definitions

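### Does the 95% Clopper-Pearson interval for disease control conflict with the one-sided 10% two-stage test?

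*Combined protocol and SAP*

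**What the plan says.** The design is in Section 13.1: "This study is a Simon (minimax) two-stage design that will enroll up to a total of 39 subjects". In stage 1, "a total of 28 subjects in the evaluable population will be enrolled". The continuation rule, given there and in Section 5.2, reads: "Of these, if at least 8 should achieve disease control (Section 13.1.1) the study will continue on to the second stage". Then: "In the second stage, 11 participants in the evaluable population (total of 39) will be enrolled". The final rule is: "If at least 16 of the 39 total subjects enrolled achieve disease control then we will be able to reject the null hypothesis". On the null value, the plan states that "a disease control rate of 30% would be considered an inferred clinical historical rate". The alternative is 50%, the test is one-sided at 0.10, and "this design will provide at least 90% power to reject the null hypothesis".

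The analysis of the primary endpoint, in Section 13.3.4.1, has two sentences. The first plans the estimate: "Disease control rate will be estimated with the corresponding 95% Clopper-Pearson confidence interval". The second says that the primary objective is judged by the rejection regions of Section 13.1. Section 13.3.4.2 plans the same kind of interval for objective response and six-month PFS.

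**The concern.** A 95% Clopper-Pearson interval, read as two-sided, puts 2.5% in each tail. Its lower limit is therefore a much stricter bound than a one-sided 10% test. It is also computed as if all 39 subjects formed one sample, without regard to the stage 1 stopping rule. Results just inside the rejection region will then reject 30% while the reported interval still contains 30%.

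Section 1.1 frames the primary objective as a comparison with a historical 30%, so readers will look for 30% in the interval. If the interval were meant to carry the conclusion, a positive trial could be reported with an interval that appears to deny it, and the team would have to choose after seeing the data which of the two to stress.

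**Working it through.** **Inputs** (Section 13.1): n1 = 28, continue at 8 or more; n = 39, reject at 16 or more; p0 = 0.30, p1 = 0.50; one-sided alpha 0.10. Section 13.3.4.1: 95% Clopper-Pearson, taken as two-sided because the text does not say.

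**1. The plan's own figures.** The probability of reaching stage 2 and ending with at least s successes is

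P(s; p) = Σ over x = 8 to 28 of Bin(x; 28, p) × Pr[Bin(11, p) ≥ s − x].

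- P(16; 0.30) = 0.0943, within the 0.10 limit.
- P(16; 0.50) = 0.9001, at least 90%.
- An exhaustive search for these error rates returns 28/39 with cut-offs 8 and 16 as the minimax design.

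The stated design reproduces.

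**2. Interval against decision.** The Clopper-Pearson lower limit is the α/2 quantile of Beta(x, n − x + 1); the upper limit is the 1 − α/2 quantile of Beta(x + 1, n − x).

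| Successes of 39 | Rate | Two-stage p at 30% | 95% interval | 80% lower limit | Decision |
|---|---|---|---|---|---|
| 15 | 38.5% | 0.1628 | 23.4% to 55.4% | 27.9% | not rejected |
| 16 | 41.0% | 0.0943 | 25.6% to 57.9% | 30.2% | rejected |
| 17 | 43.6% | 0.0500 | 27.8% to 60.4% | 32.6% | rejected |
| 18 | 46.2% | 0.0242 | 30.1% to 62.8% | 35.0% | rejected |

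Only 16 and 17 are discordant. They are the two results whose p-value lies between 0.025 and 0.10, where a 10% test rejects and a 2.5% bound does not exclude. The discordance runs one way: no result puts the 95% lower limit above 30% without also rejecting.

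**3. How often.** P(16; p) − P(18; p) gives:

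- 0.0943 − 0.0242 = 0.070 at a true rate of 30%;
- 0.508 − 0.265 = 0.243 at 40%;
- 0.900 − 0.739 = 0.161 at 50%, or 0.161/0.900 = 18% of rejections, so about 82% are concordant.

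The 7.0 points at 30% show where false rejections fall. The interval does not cause them.

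**4. Does ignoring the stopping rule matter?** Solving P(s; p) = a for p gives two-stage lower limits to set beside the ordinary ones:

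- 2.5% bound at 16/39: 0.25567 ordinary, 0.25570 two-stage; at 17/39: 0.27811 for both.
- 10% bound at 16/39: 0.30231 ordinary, 0.30235 two-stage.
- p-value at 16/39: 0.0944 single-stage, 0.0943 two-stage.
- Estimate at 16/39: 0.4103 raw proportion, 0.4106 minimum-variance unbiased.

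The stopping rule is immaterial here because a trial that stops with 7 or fewer of 28 would very rarely have reached 16 of 39. The gap comes from the confidence level alone.

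**5. Is the interval valid under the two-stage design?** Exact coverage is 95.1% to 97.4% at true rates from 20% to 70% in steps of five points. It does not under-cover.

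**The case for a change.** The best case for acting is this. The objective is comparative, the plan gives only one interval, and it neither calls that interval descriptive nor says how to report a rejection whose interval contains 30%. The Statistical Analysis row of the Protocol Summary mentions the interval and leaves out the rejection rule. At a true rate of 40%, almost half of the rejections (0.243 of 0.508, or 48%) would look discordant. An 80% interval would agree with the rule on both sides of the boundary, with lower limits of 27.9% at 15/39 and 30.2% at 16/39, and would cost one sentence.

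The figures stand, and so does the observation that the plan does not explain why the two levels differ. It does not follow that the plan is ambiguous. Section 13.3.4.1 names the basis of the decision immediately after the interval, and the rule is a count fixed in advance, so no choice remains to be made after the data are seen. An 80% interval would restate that count on another scale. A two-stage limit, a two-stage p-value or an unbiased estimator would differ from the ordinary quantities only in the fourth decimal place or beyond. Some statisticians match the interval to the test level; others report 95% throughout, as this plan does for its other binary endpoints. Either is sound.

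**Conclusion.** The concern does not hold. The plan separates the decision, a count against a fixed rejection region, from estimation, a 95% interval, and says which of them settles the primary objective. Type I error (0.0943), power (0.9001) and the stage 1 rule do not depend on the interval. At 16 or 17 of 39 the interval contains 30% because a result with one-sided p of 0.094 or 0.050 is modest evidence. A screening test at 10% accepts such evidence and a 95% interval shows its limits; both statements are true together.

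This rests on reading the interval as two-sided, on a final analysis of exactly 39 evaluable subjects, and on the decision being taken from Section 13.1 as Section 13.3.4.1 directs. If a report drew the primary conclusion from the interval instead, it would depart from the plan; the plan itself would not be at fault.

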13.3.4.2. Secondary Analyses

Objective response rate and 6-month PFS rate will be estimated with the corresponding 95% Clopper-Pearson confidence interval.

Progression-free survival and overall survival rates will be estimated using Kaplan-Meier techniques.

Multivariable regression models (logistic regression for binary variables and Cox proportional hazards models for time to event variables) will be used to evaluate the impact of correlative biomarkers, and baseline subject and disease characteristics on outcomes. Additionally, nintedanib exposure will be considered as a covariate.

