13.2. Analysis Populations

The response-evaluable population for the analysis of objective response will include enrolled subjects with measurable disease at baseline. The evaluable population for the analysis of disease control, all other secondary endpoints, and safety endpoints will include subjects who begin nintedanib treatment. The sample size requirements for

Stage 1 and 2 described above pertain to the evaluable population for the analysis of disease control.

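### Objective response will probably be too sparse for the planned multivariable logistic model; name Firth penalised likelihood for the binary outcomes and analyse response one covariate at a time

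*Combined protocol and SAP*

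**What the plan says.** Section 13.3.4.2 of the combined protocol and SAP commits to regression for all outcomes: "Multivariable regression models (logistic regression for binary variables and Cox proportional hazards models for time to event variables) will be used". The candidate predictors are correlative biomarkers and baseline subject and disease characteristics, and nintedanib exposure may also be a covariate. Item I of the Protocol Summary repeats the commitment for baseline characteristics.

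Three binary outcomes are defined: disease control (13.1.1), objective response (13.1.2) and six-month PFS (13.1.4). For objective response, Section 13.2 narrows the population: "The response-evaluable population for the analysis of objective response will include enrolled subjects with measurable disease at baseline". Inclusion criterion f in Section 4.2.1 also admits subjects who have only non-measurable disease, so this group may be smaller than the whole trial.

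On size, Section 13.1 says: "This study is a Simon (minimax) two-stage design that will enroll up to a total of 39 subjects" and "In the first stage, a total of 28 subjects in the evaluable population will be enrolled". The trial goes on only if at least 8 of those 28 achieve disease control.

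The plan sets no covariate list or limit, no minimum number of events, no estimator, and no fallback if a model cannot be fitted. It states no expected objective response rate.

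**The concern.** A logistic model fitted by ordinary maximum likelihood needs enough subjects in the rarer outcome class. When a covariate, or a combination of covariates, splits responders from non-responders perfectly or nearly so, the likelihood has no finite maximum and the odds ratio runs off to infinity (separation). When the model does fit in a small sample, coefficients for real associations are biased away from the null.

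The regressions are placed among the secondary analyses and nothing labels them exploratory, although serum and ascites VEGF are exploratory objectives in Section 1.3. Section 2.1 reports that nothing beyond case reports was found for second-line treatment, so an overstated predictor from this trial could carry undue weight. If an ordinary model fails and no fallback was specified, the replacement will be chosen after seeing the data.

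**Working it through.** **1. The plan's own figures.** The plan gives none for the regressions. Its design figures reproduce. Let b(x; 28, p) be the binomial probability of x controlled subjects among the first 28, and Y the number among the next 11. The probability of rejection is the sum over x = 8 to 28 of b(x; 28, p) × P(Y ≥ 16 − x). At p = 0.30 it is 0.0943 (limit 0.10). At p = 0.50 it is 0.9001 (target at least 0.90). The chance of stopping at Stage 1 under 30% is P(X ≤ 7 of 28) = 0.365.

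**2. Size of the rarer class.** With 39 subjects it cannot exceed 19. Expected disease control is 39 × 0.30 = 11.7 under the null and 39 × 0.50 = 19.5 under the alternative. After a Stage 1 stop, at most 7 of 28 subjects have disease control.

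**3. Objective response: why separation is likely.** Assume 30 measurable subjects and a response rate of 5% to 20%. The only pointer in the documents to a low rate is the single confirmed partial response in the single-agent lung cancer study in Section 2.2.2.

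Take one evenly split binary covariate unrelated to response. The chance that all r responders fall in the same level is 2 × 0.5^r. That is 0.50 for r = 2 and 0.25 for r = 3, and it is certain for r = 1. Each such case has an infinite estimate, and adding covariates only raises the chance.

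**4. Objective response: simulated failure rates.** Covariates were half binary (evenly split) and half normal. A trial failed if it had no responders or showed separation, which was checked by linear programming. There were 400 to 2,000 trials per setting.

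| Assumed response rate | Expected responders of 30 | Chance of none | No finite estimate, 2 covariates | No finite estimate, 4 covariates |
|---|---|---|---|---|
| 5% | 1.5 | 0.95^30 = 0.215 | about 70% to 75% | about 82% to 87% |
| 10% | 3.0 | 0.90^30 = 0.042 | about 40% | about 53% to 62% |
| 20% | 6.0 | 0.80^30 = 0.001 | about 9% | not tabulated |

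If all 39 subjects are measurable, with 2 to 8 balanced covariates, failures are 65% to 95% at a 5% response rate, 29% to 75% at 10% and 5% to 35% at 20%.

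**5. Disease control, 39 subjects, rate 30% to 50%.** With up to 5 balanced covariates, 0% to 3% of trials fail. Where the model fits and the true odds ratio is 2.0 (log 0.693), the geometric mean odds ratios are:
- 2 covariates, maximum likelihood: 2.13 to 2.15.
- 4 covariates at 50%, maximum likelihood: mean log 0.834, so exp(0.834) = 2.30. Firth: exp(0.708) = 2.03.
- 6 covariates at 50%, maximum likelihood: exp(0.933) = 2.54, and 2.75 in a separate set of runs. Firth: exp(0.736) = 2.09.

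With a true odds ratio of 1 there is essentially no bias. At nominal 5%, the likelihood-ratio test rejects in 5.3% to 6.2% of trials with 2 covariates and 6.5% to 8.1% with 4 to 6. The Wald test on the same data rejects in 4.6% to 6.0%.

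**6. Sensitivity.** If one covariate has a level held by only 10% of subjects, disease-control models with 3 to 8 covariates fail in 27% to 35% of trials at rates of 30% to 50%. With 28 subjects and a 25% rate they fail in 52% to 70%.

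**7. Limits of Firth.** It returned a fit in the separated data sets too, given at least one event and one non-event. At event rates of 5% to 10%, however, a true odds ratio of 2 averaged about 1.5 to 2.3, with shrinkage as covariates were added. That is why objective response should be taken one covariate at a time.

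**The case against.** Several parts of the opposing case stand.

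- The plan says logistic regression and names no estimator. Penalised or exact fitting is not excluded, so the failure rates describe the usual default rather than something the text demands.
- Few responders is an assumption. No response rate is stated, and at 20% the failure rate with 2 covariates is modest.
- A reader might infer that the models break down for every binary outcome. They do not: disease control at 30% to 50% with a few balanced covariates nearly always fits. Six-month PFS would behave the same way at similar rates, but no rate is stated for it. Trouble there needs many covariates or a sparse level.
- A reader might infer that chance predictors would commonly be reported. The type I excess is small and appears with the likelihood-ratio test but hardly with the Wald test. The plan specifies neither a test nor a significance level for these models, and inflation does not create an association where none exists.
- A reader might want a cap of one covariate per 10 events. With at most 19 in the rarer class it would never allow two covariates for any binary outcome, and with 3 responders it would allow none. It would abolish the models rather than repair them.
- A reader might extend the point to the Cox models. No Cox calculation supports that. Section 13.3.1 ties the final analysis to 20% PFS censoring (about 0.80 × 39 = 31 events) or 3 years, so PFS may be far less sparse.

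What does not fall away is the objective response model, whose estimability is poor across the 5% to 10% range, and the avoidable inflation in the disease-control models.

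**Conclusion.** The point holds in a limited form. For objective response, if 5% to 10% of about 30 measurable subjects respond, an ordinary logistic model with 2 to 4 covariates has no finite estimate in roughly 40% to 85% of trials. For disease control at 30% to 50% the model usually fits, but a true odds ratio of 2.0 is reported on average as about 2.1 to 2.3 with 2 to 4 covariates and about 2.5 or more with 6. Likelihood-ratio type I error is then about 6% to 8% with 4 to 6 covariates, and there is no bias at a true odds ratio of 1.

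These sizes rest on assumed response rates, numbers of measurable subjects, covariate counts and covariate distributions, because the documents give none of them.

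The documents do not support reading this as a threat to the trial's conclusion. The primary decision uses the rejection regions of Section 13.1, and the response and six-month PFS rates have Clopper-Pearson intervals. None of these depends on the regressions. This is a worthwhile improvement to a secondary analysis and not an essential correction.

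**What to change.** Amend Section 13.3.4.2 to state that:

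- logistic models for the binary outcomes will be fitted by Firth penalised likelihood, with profile-likelihood intervals;
- objective response will be examined one covariate at a time, by Firth or exact methods;
- the regression results are exploratory.

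No covariate cap tied to event counts is needed, and the Cox models can stay as planned.

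The cost is a few sentences in the plan and standard software. Sample size, data collection and the primary test do not change. The downside is slight shrinkage of estimates and no joint adjustment for objective response. If there are no responders at all, no method can estimate an association, and only the rate and its interval can be reported.

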13.3.5. Safety Analyses

Treatment administration will be summarized descriptively in terms of cumulative and average daily dose of nintedanib administration (adjusting for dose delays and reductions). Additionally, the relative dose intensity will be calculated in terms of the actual daily dose administered as a percent of the intended daily dose. Incident rates for treatment-emergent adverse events, SAEs, and deaths while on study therapy will be summarized.

Treatment-emergent adverse events are defined as follows:

- An adverse event that occurs after treatment start that was not present at the time of treatment start; or
- An adverse event that increases in severity after treatment start if the event was present at the time of treatment start

13.3.6. Exploratory Analyses

An evaluation of serum VEGF, ascites VEGF, hypertension and paracentesis frequency will be made. This will include summaries of expression levels, baseline prevalence, and correlations between these biomarkers and response to therapy. Additional exploratory analysis will be conducted as deemed necessary.

13.4. Interim Analyses

An analysis of disease control will be conducted after the best overall response of the first 28 evaluable participants has been determined.

14. STUDY COMPLETION

14.1. Completion

The study will be considered complete when one or more of the following conditions is met:

- All subjects have died and/or withdrawn from the study.
- All subjects have discontinued from the study.
- The IRB, LCI DSMC, or Sponsor-Investigator discontinues the study because of safety considerations.
- The Sponsor-Investigator defines an administrative or clinical cut-off date.

14.2. Termination

The study will be terminated when one or more of the following conditions occur:

If risk-benefit ratio becomes unacceptable owing to, for example,

- Safety findings from this study (e.g. SAEs)
- Results of any interim analysis
- Results of parallel clinical studies
- Results of parallel animal studies (e.g. toxicity, teratogenicity, carcinogenicity or reproduction toxicity).
- If the study conduct (e.g. recruitment rate; drop-out rate; data quality; protocol compliance) does not suggest a proper completion of the trial within a reasonable time frame.

The Sponsor-Investigator has the right to close the trial at any site and at any time.

For any of the above closures, the following applies:

- Closures should occur only after consultation between involved parties.
- All affected institutions must be informed as applicable according to local law.
- In case of a partial study closure, ongoing subjects, including those in follow-up, must be taken care of in an ethical manner.

Details for individual subject's withdrawal can be found in Section 5.4.2.

15. RETENTION OF RECORDS

Essential documentation (e.g. adverse events, records of study drug receipt and dispensation), including all IRB correspondence, will be retained for at least 2 years after the investigation is completed. Documentation will be readily available upon request.

